2.3.7. WITHDRAWAL OF PATIENTS FROM THERAPY OR ASSESSMENT

Patient is, at any time, free to withdraw from study (investigational product and study assessments), without prejudice to further treatment (withdrawal of consent). Subjects that choose to withdraw early from the study will be voluntarily surveyed for reasons for withdrawal, including information of possible presence of any adverse events. If possible, he/she will be seen and assessed by an investigator.

Adverse events will be followed up and all study material (if any) should be returned by the patient. The investigator may also, at his/her discretion, withdraw the subject from participating in this study at any time, or the sponsor may discontinue the study. Withdrawn patient will not be replaced.

If any patient stopped the study treatment prematurely (before the 6 cycles), it will be listed below along with his/her details.

Table 146. Study treatment premature interruption

		N (% , CI95%)
Study treatment premature interruption	Yes	
	No	
Reasons for study treatment premature interruption	Reason 1	
	Reason 2	
	Reason 3	
	...	

Details of the end of treatment reasons will be shown in the following table.

Table 147. Reason for end of treatment for Cabozantinib

		N (% , CI95%)
Progression		
Unaccepted toxicity	Toxicity 1	
Details of toxicities	Toxicity 2	
	
AE not related to the treatment study		
Investigator decision	Investigator decision 1	
Details of investigator decisions	Investigator decision 1	
	...	
Withdraw consent	Other reasons 1	
Other reasons	Other reasons 2	
Details of other reasons	...	
Patients with treatment completion		

Sponsor: Grupo Español de Tumores Neuroendocrinos y Endocrinos (GETNE)

Table 148. Reason for end of treatment for Atezolizumab

Reasons for end of treatment	N (% , CI95%)		
Progression			
Unaccepted toxicity			
Details of toxicities	Toxicity 1		
	Toxicity 2		
		
AE not related to the treatment study			
Investigator decision	Investigator decision 1		
Details of investigator decisions	Investigator decision 1		
		
Withdraw consent	Other reasons 1		
Other reasons	Other reasons 2		
Details of other reasons		
Patients with treatment completion	N	Mean, SD (CI95%)	Median (CI95%) [Range]
Induction cycles received			

The median of the study treatment was XXX weeks:

Table 149. Study treatment length

Length of study treatment (months)	N	Mean, SD (CI95%)	Median (CI95%) [Range]

2.3.7.1 WITHDRAWAL OF PATIENTS FROM THERAPY OR ASSESSMENT IN COHORT 1

Details of the withdrawal of patients in cohort 1 are shown below:

Table 150. Study treatment premature interruption in cohort 1

	N (% , CI95%)
Study treatment premature interruption	Yes
	No
Reasons for study treatment premature interruption	Reason 1
	Reason 2
	Reason 3
	...

Details of the end of treatment reasons will be shown in the following table.

Sponsor: Grupo Español de Tumores Neuroendocrinos y Endocrinos (GETNE)

Table 151. Reason for end of treatment for Cabozantinib in cohort 1

		N (% , CI95%)
Reasons for end of treatment	Progression	
	Unaccepted toxicity	
	Details of toxicities	Toxicity 1
		Toxicity 2
	
	AE not related to the treatment study	
	Investigator decision	
	Details of investigator decisions	Investigator decision 1
		Investigator decision 1
		...
Withdraw consent		
Other reasons		
Details of other reasons	Other reasons 1	
	Other reasons 2	
	...	
Patients with treatment completion		

Table 152. Reason for end of treatment for Atezolizumab in cohort 1

		N (% , CI95%)
Reasons for end of treatment	Progression	
	Unaccepted toxicity	
	Details of toxicities	Toxicity 1
		Toxicity 2
	
	AE not related to the treatment study	
	Investigator decision	
	Details of investigator decisions	Investigator decision 1
		Investigator decision 1
		...
Withdraw consent		
Other reasons		
Details of other reasons	Other reasons 1	
	Other reasons 2	
	...	
Patients with treatment completion		
	N	Mean, SD (CI95%)
Induction cycles received		Median (CI95%) [Range]

The median of the study treatment was XXX weeks:

Table 153. Study treatment length in cohort 1

N	Mean, SD (CI95%)	Median (CI95%) [Range]

Sponsor: Grupo Español de Tumores Neuroendocrinos y Endocrinos (GETNE)

**Length of study treatment
(months)**

2.3.7.2 WITHDRAWAL OF PATIENTS FROM THERAPY OR ASSESSMENT IN COHORT 2

Details of the withdrawal of patients in cohort 2 are shown below:

Table 154. Study treatment premature interruption in cohort 2

		N (%), CI95%
Study treatment premature interruption	Yes	
	No	
	Reason 1	
Reasons for study treatment premature interruption	Reason 2	
	Reason 3	
	...	

Details of the end of treatment reasons will be shown in the following table.

Table 155. Reason for end of treatment for Cabozantinib in cohort 2

		N (%), CI95%
Reasons for end of treatment	Progression	
	Unaccepted toxicity	
		Toxicity 1
	Details of toxicities	Toxicity 2
	
	AE not related to the treatment study	
	Investigator decision	
		Investigator decision 1
	Details of investigator decisions	Investigator decision 1
		...
	Withdraw consent	
	Other reasons	
		Other reasons 1
	Details of other reasons	Other reasons 2
		...
Patients with treatment completion		

Table 156. Reason for end of treatment for Atezolizumab in cohort 2

		N (%), CI95%
Reasons for end of treatment	Progression	
	Unaccepted toxicity	
		Toxicity 1
	Details of toxicities	Toxicity 2
	

Sponsor: Grupo Español de Tumores Neuroendocrinos y Endocrinos (GETNE)

AE not related to the treatment study	
Investigator decision	
	Investigator decision 1
Details of investigator decisions	Investigator decision 1
	...
Withdraw consent	
Other reasons	
	Other reasons 1
Details of other reasons	Other reasons 2
	...
Patients with treatment completion	
	N
	Mean, SD (CI95%)
Induction cycles received	
	Median (CI95%) [Range]

The median of the study treatment was **XXX** weeks:

Table 157. Study treatment length in cohort 2

	N	Mean, SD (CI95%)	Median (CI95%) [Range]
Length of study treatment (months)			

2.3.7.3 WITHDRAWAL OF PATIENTS FROM THERAPY OR ASSESSMENT IN COHORT 3

Details of the withdrawal of patients in cohort 3 are shown below:

Table 158. Study treatment premature interruption in cohort 3

		N (% , CI95%)
Study treatment premature interruption	Yes	
	No	
	Reason 1	
Reasons for study treatment premature interruption	Reason 2	
	Reason 3	
	...	

Details of the end of treatment reasons will be shown in the following table.

Table 159. Reason for end of treatment for Cabozantinib in cohort 3

		N (% , CI95%)
Reasons for end of treatment	Progression	
	Unaccepted toxicity	
	Details of toxicities	Toxicity 1
		Toxicity 2

Sponsor: Grupo Español de Tumores Neuroendocrinos y Endocrinos (GETNE)

AE not related to the treatment study	
Investigator decision	
	Investigator decision 1
Details of investigator decisions	Investigator decision 1

Withdraw consent	
Other reasons	
	Other reasons 1
Details of other reasons	Other reasons 2

Patients with treatment completion	

Table 160. Reason for end of treatment for Atezolizumab in cohort 3

Reasons for end of treatment	N (% , CI95%)		
	Progression		
	Unaccepted toxicity		
		Toxicity 1	
	Details of toxicities	Toxicity 2	
		
	AE not related to the treatment study		
	Investigator decision		
		Investigator decision 1	
	Details of investigator decisions	Investigator decision 1	
		
	Withdraw consent		
	Other reasons		
		Other reasons 1	
	Details of other reasons	Other reasons 2	
		
Patients with treatment completion	N	Mean, SD (CI95%)	Median (CI95%) [Range]
Induction cycles received			

The median of the study treatment was XXX weeks:

Table 161. Study treatment length in cohort 3

	N	Mean, SD (CI95%)	Median (CI95%) [Range]
Length of study treatment (months)			

Sponsor: Grupo Español de Tumores Neuroendocrinos y Endocrinos (GETNE)

2.3.7.4 WITHDRAWAL OF PATIENTS FROM THERAPY OR ASSESSMENT IN COHORT 4

Details of the withdrawal of patients in cohort 4 are shown below:

Table 162. Study treatment premature interruption in cohort 4

		N (% , CI95%)
Study treatment premature interruption	Yes	
	No	
	Reason 1	
Reasons for study treatment premature interruption	Reason 2	
	Reason 3	
	...	

Details of the end of treatment reasons will be shown in the following table.

Table 163. Reason for end of treatment for Cabozantinib in cohort 4

		N (% , CI95%)
Reasons for end of treatment	Progression	
	Unaccepted toxicity	
		Toxicity 1
	Details of toxicities	Toxicity 2
	
	AE not related to the treatment study	
	Investigator decision	
		Investigator decision 1
	Details of investigator decisions	Investigator decision 1
		...
	Withdraw consent	
	Other reasons	
		Other reasons 1
	Details of other reasons	Other reasons 2
		...
Patients with treatment completion		

Table 164. Reason for end of treatment for Atezolizumab in cohort 4

		N (% , CI95%)
Reasons for end of treatment	Progression	
	Unaccepted toxicity	
		Toxicity 1
	Details of toxicities	Toxicity 2
	
	AE not related to the treatment study	
	Investigator decision	
		Investigator decision 1
	Details of investigator decisions	Investigator decision 1

Sponsor: Grupo Español de Tumores Neuroendocrinos y Endocrinos (GETNE)

Investigator decision 1		
...		
Withdraw consent		
Other reasons		
Details of other reasons	Other reasons 1	
	Other reasons 2	
...		
Patients with treatment completion		
N	Mean, SD (CI95%)	Median (CI95%) [Range]
Induction cycles received		

The median of the study treatment was **XXX** weeks:

Table 165. Study treatment length in cohort 4

N	Mean, SD (CI95%)	Median (CI95%) [Range]
Length of study treatment (months)		

2.3.7.5 WITHDRAWAL OF PATIENTS FROM THERAPY OR ASSESSMENT IN COHORT 5

Details of the withdrawal of patients in cohort 5 are shown below:

Table 166. Study treatment premature interruption in cohort 5

		N (% CI95%)
Study treatment premature interruption	Yes	
	No	
Reasons for study treatment premature interruption	Reason 1	
	Reason 2	
	Reason 3	
	...	

Details of the end of treatment reasons will be shown in the following table.

Table 167. Reason for end of treatment for Cabozantinib in cohort 5

			N (% CI95%)
	Progression		
	Unaccepted toxicity		
		Toxicity 1	
Reasons for end of treatment	Details of toxicities	Toxicity 2	
		
	AE not related to the treatment study		
	Investigator decision		
	Details of investigator decisions	Investigator decision 1	

Sponsor: Grupo Español de Tumores Neuroendocrinos y Endocrinos (GETNE)

	Investigator decision 1
	...
Withdraw consent	
Other reasons	
Details of other reasons	Other reasons 1 Other reasons 2 ...
Patients with treatment completion	

Table 168. Reason for end of treatment for Atezolizumab in cohort 5

Reasons for end of treatment	N (% , CI95%)		
	Progression		
	Unaccepted toxicity		
	Details of toxicities	Toxicity 1 Toxicity 2	
	AE not related to the treatment study		
	Investigator decision		
	Details of investigator decisions	Investigator decision 1 Investigator decision 1 ...	
	Withdraw consent		
	Other reasons		
	Details of other reasons	Other reasons 1 Other reasons 2 ...	
Patients with treatment completion	N	Mean, SD (CI95%)	Median (CI95%) [Range]
Induction cycles received			

The median of the study treatment was XXX weeks:

Table 169. Study treatment length in cohort 5

Length of study treatment (months)	N	Mean, SD (CI95%)	Median (CI95%) [Range]

2.3.7.6 WITHDRAWAL OF PATIENTS FROM THERAPY OR ASSESSMENT IN COHORT 6

Details of the withdrawal of patients in cohort 6 are shown below:

Table 170. Study treatment premature interruption in cohort 6

Yes	N (% , CI95%)

Sponsor: Grupo Español de Tumores Neuroendocrinos y Endocrinos (GETNE)

Study treatment premature interruption	No
	Reason 1
Reasons for study treatment premature interruption	Reason 2
	Reason 3
	...

Details of the end of treatment reasons will be shown in the following table.

Table 171. Reason for end of treatment for Cabozantinib in cohort 6

	N (% , CI95%)
Reasons for end of treatment	
Progression	
Unaccepted toxicity	
	Toxicity 1
Details of toxicities	Toxicity 2

AE not related to the treatment study	
Investigator decision	
	Investigator decision 1
Details of investigator decisions	Investigator decision 1
	...
Withdraw consent	
Other reasons	
	Other reasons 1
Details of other reasons	Other reasons 2
	...
Patients with treatment completion	

Table 172. Reason for end of treatment for Atezolizumab in cohort 6

	N (% , CI95%)
Reasons for end of treatment	
Progression	
Unaccepted toxicity	
	Toxicity 1
Details of toxicities	Toxicity 2

AE not related to the treatment study	
Investigator decision	
	Investigator decision 1
Details of investigator decisions	Investigator decision 1
	...
Withdraw consent	
Other reasons	
	Other reasons 1
Details of other reasons	Other reasons 2
	...
Patients with treatment completion	

Sponsor: Grupo Español de Tumores Neuroendocrinos y Endocrinos (GETNE)

	N	Mean, SD (CI95%)	Median (CI95%) [Range]
Induction cycles received			

The median of the study treatment was XXX weeks:

Table 173. Study treatment length in cohort 6

	N	Mean, SD (CI95%)	Median (CI95%) [Range]
Length of study treatment (months)			

Sponsor: Grupo Español de Tumores Neuroendocrinos y Endocrinos (GETNE)

2.4. ANALYSIS SETS

As defined in the protocol, all efficacy analyses will be based primarily on the Intention-to treat (ITT) analysis set and secondarily on the Per Protocol (PP) analysis set, which are defined as follows:

- ITT analysis set: All patients who were enrolled (included) in the trial.
- PP analysis set: All patients fulfilling all eligibility criteria without any protocol deviation that makes patient invalid for the primary endpoint evaluation.

And the safety analysis set is defined as:

- Any patient included in the study receiving at least a single dose of study medication will be evaluable for the toxicity analysis.

Table 174. Analysis sets

	N (%)
ITT population	Yes No
PP population	Yes No
Safety population	Yes No

If any patient is excluded either from the ITT, PP and/or security population, it will be listed below along with the reasons why:

Table 175. List of patients that are excluded from ITT, PP and/or security population

Patient ID	ITT code	Reason excluded form population	PP population	Reason excluded form population	Security population	Reason excluded form population

Sponsor: Grupo Español de Tumores Neuroendocrinos y Endocrinos (GETNE)

2.5. EFFICACY ANALYSIS

Both ITT and PP populations will be used to present the efficacy analysis.

2.5.1. PRIMARY EFFICACY ANALYSIS

Overall Response Rate (ORR): includes patients with confirmed partial (PR) and complete response (CR) as best response according to RECIST v 1.1.

The ORR is the proportion of patients with tumor size reduction (CR or PR), recorded between the date of the first dose and the last tumor evaluation before starting a subsequent treatment of each patient in the study. The proportion of response rates will be expressed with the 95% confidence interval.

The Overall response rate by RECIST in the ITT population (n=XX) is shown in the following table:

Table 176. ORR (ITT)

	Cohort 1 N (%), CI95%	Cohort 2 N (%), CI95%	Cohort 3 N (%), CI95%	Cohort 4 N (%), CI95%	Cohort 5 N (%), CI95%	Cohort 6 N (%), CI95%
ORR						
CR						
PR						
SD						
PD						
Total	n (100%)					
CR or PR						
SD or PD						
Total	n 100%	n (100%)				

The Overall response rate by RECIST in the PP population (n=XX) is shown in the following table:

Table 177. ORR (PP)

	Cohort 1 N (%), CI95%	Cohort 2 N (%), CI95%	Cohort 3 N (%), CI95%	Cohort 4 N (%), CI95%	Cohort 5 N (%), CI95%	Cohort 6 N (%), CI95%
ORR						
CR						
PR						
SD						
PD						
Total	n (100%)					
CR or PR						
SD or PD						
Total	n 100%	n (100%)				

Sponsor: Grupo Español de Tumores Neuroendocrinos y Endocrinos (GETNE)

2.5.2. SECONDARY EFFICACY ANALYSIS

Duration of response (DOR) as per RECIST 1.1: DOR calculated as the time from the date of first documented CR or PR to the first documented progression or death due to underlying cancer.

Progression-free Survival (PFS): Median Progression free survival (mPFS) is defined as the time from the date of inclusion to the date of the first documented disease progression or death due to any cause, whichever occurs first. PFS will be determined based on tumour assessment (RECIST version 1.1 criteria).

Overall Survival (OS): Median Overall Survival (mOS) is calculated as the time from date of inclusion to date of death due to any cause.

Biomarkers: To be determined according to study results and Sponsor feasibility.

2.5.2.1 DURATION OF RESPONSE

Duration of response (DOR) as per RECIST in the ITT set is shown in the following table:

Table 178. Duration of response (DOR) (ITT)

Duration of Response (months)	n	Mean (SD)	Median (IQR)	Min-Max	CI95% of the mean
Cohort1					
Cohort 2					
Cohort 3					
Cohort 4					
Cohort 5					
Cohort 6					
Total					

Duration of response (DOR) as per RECIST in the PP set is shown in the following table:

Table 179. Duration of response (DOR) (PP)

Duration of Response (months)	n	Mean (SD)	Median (IQR)	Min-Max	CI95% of the mean
Cohort1					
Cohort 2					
Cohort 3					
Cohort 4					
Cohort 5					
Cohort 6					
Total					

Sponsor: Grupo Español de Tumores Neuroendocrinos y Endocrinos (GETNE)

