8.2.4.2. Overall Survival (Long term follow-up)

Follow-up after disease progression will be carried out according to local practice. The follow-up period according to this protocol is 12 months considering last patient inclusion. Information on subsequent treatments should include the list of post-treatment therapies, the drugs administered, the date of initiation/discontinuation of each drug and date of progression. All the data will be recorded in the medical record and in the eCRF.

Survival information may be obtained through telephone contact with the patient, patient's family or by contact with the patient's current physician. Survival data will be collected up to the time of the final overall survival (OS) analysis, and at this point, Investigators will be notified that no further data collection for the study is required.

The status of ongoing, withdrawn (from the study), and lost to follow-up patients at the time of an OS analysis should be obtained by the site personnel by checking the patient's notes and hospital records, contacting the patient's general clinician, and checking publicly available death registries.

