1.2.2. ENDPOINTS

Primary endpoint:

Overall Response Rate (ORR): includes patients with confirmed partial (PR) and complete response (CR) as best response according to RECIST v 1.1.

Secondary endpoints:

- **Safety profile of cabozantinib and atezolizumab:** The number of patients with AEs and SAEs, changes in laboratory values, vital signs, ECGs, and results of physician examinations graded according to the CTCAE v 5.0. This will be analysed using descriptive statistics techniques such as frequency and contingency tables. The final statistical analysis of this endpoint is expected to be performed within 6 months after database closure, which is expected at 12 months after last patient inclusion. However, interim analysis may be performed when analysing other primary endpoints.
- **Duration of response (DOR) as per RECIST 1.1:** DOR calculated as the time from the date of first documented CR or PR to the first documented progression or death due to underlying cancer.
- **Progression-free Survival (PFS):** Median Progression free survival (mPFS) is defined as the time from the date of inclusion to the date of the first documented disease progression or death due to any cause, whichever occurs first. PFS will be determined based on tumour assessment (RECIST version 1.1 criteria). The local Investigator's assessments will be used for analyses. Patients who are alive and have not progressed at the last follow-up will be censored at the date of the last available image determination (CT Scan or MRI). Patient with no additional image test other than that at baseline will be censored to the day after inclusion.
- **Overall Survival (OS):** Median Overall Survival (mOS) is calculated as the time from date of inclusion to date of death due to any cause.
- **Biomarkers:** To be determined according to study results and Sponsor feasibility.

Sponsor: Grupo Español de Tumores Neuroendocrinos y Endocrinos (GETNE)

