1.4.2. GENERAL CONSIDERATIONS

'Last patient last visit', as defined in the protocol, is 12 months after the enrolment of last patient. Subjects may continue to receive IMPs after the cut-off because treatment cannot be discontinued for ethical reasons, but in such cases, Sponsor agrees to continue with cabozantinib supply to sites to cover patient treatment until its finalisation and atezolizumab for a maximum of 6 months after the end of the study (LPLV). For these 6 additional months (since LPLV), the principal investigators must inform on any suspicion on adverse events/special situations in patients receiving atezolizumab's, to the marketing authorisation holder.

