1.5. SUMMARY OF STUDY DATA

For each categorical variable, the results will be summarised by frequencies and percentages. For each continuous variable, the results will be summarised by descriptive statistics such as median, range, and interquartile range or by means, standard deviations, and 95 % confidence intervals (CIs). For proportions, point estimates and exact 95 % confidence intervals will be calculated. For time to event endpoints, Kaplan-Meier estimates at selected time points and corresponding curves will be presented. Time to event is derived relative to the first study treatment administration. Laboratory values will be expressed as absolute values and in grades (ordinal categorical variables) according to NCI CTCAE v 5.0.

Treatment-emergent AE (AEs starting after the administration of study treatment and up to study completion) will be summarised by system organ class and preferred term. Grading will be presented by type and in tables showing the frequency and percentage of the within-patient worst grades. In addition, grade ≥ 3 AEs will be summarised separately. Full analysis details will be outlined in the statistical analysis plan (SAP).

Sponsor: Grupo Español de Tumores Neuroendocrinos y Endocrinos (GETNE)

Continuous data will be presented with the number of observations, mean value, standard deviation, minimum, maximum, and median. Categorical data will be presented as counts and percentages. Individual subject data will be listed.

Vital signs, ECG parameters, clinical laboratory data (haematology, serum biochemistry, and urinalysis) will be presented in tabular form. Values outside the reference range will be flagged, and the clinically significantly abnormal values will be listed in tabular form. Adverse events will be tabulated by system organ class and preferred term after medical coding using the according to NCI CTCAE v 5.0.

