2.5.2.2 PROGRESSION FREE SURVIVAL

The 6 months progression-free survival rate will be estimated and plotted using the Kaplan-Meier product-limit method, along with their corresponding log-log transformed 95% confidence intervals.

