2.5.2.3 OVERALL SURVIVAL

The overall survival rate will be estimated and plotted using the Kaplan-Meier product-limit method, along with their corresponding log-log transformed 95% confidence intervals.

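### The SAP's duration-of-response tables use an ordinary mean, SD and CI of the mean instead of the Kaplan-Meier estimates the SAP promises for time-to-event endpoints, and DoR has no censoring date

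*Combined protocol and SAP*

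**What the plan says.** DoR is a secondary endpoint, defined identically in the protocol (synopsis and section 10.2.2) and the SAP (sections 1.2.2 and 2.5.2). It runs from the first documented CR or PR to progression or death from the underlying cancer.

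SAP section 2.5.2.1 gives the two shells, Table 178 (ITT) and Table 179 (PP). The columns are n, mean (SD), median (IQR), min-max and "CI95% of the mean".

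The general rule in SAP section 1.5, repeated in protocol section 10.6, reads: "For time to event endpoints, Kaplan-Meier estimates at selected time points and corresponding curves will be presented". It does not name DoR.

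For PFS (SAP 2.5.2.2) the 6-month rate "will be estimated and plotted using the Kaplan-Meier product-limit method". For OS (SAP 2.5.2.3): "The overall survival rate will be estimated and plotted using the Kaplan-Meier product-limit method". The PFS and OS tables carry events, patients at risk, a median with standard error and 95% CI, and a Kaplan-Meier footnote. The SAP's list of figures has four Kaplan-Meier curves: PFS and OS, each in ITT and PP.

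The only written censoring date is inside the PFS definition: event-free patients "will be censored at the date of the last available image determination".

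On follow-up, protocol section 8.2.4.2 says: "The follow-up period according to this protocol is 12 months considering last patient inclusion". SAP section 1.4.2 adds: "Subjects may continue to receive IMPs after the cut-off because treatment cannot be discontinued for ethical reasons".

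**The concern.** DoR is a time-to-event endpoint by its definition, so the general Kaplan-Meier rule should reach it. The DoR shells do not follow that rule. An ordinary mean, SD and confidence interval of the mean need a completed duration for every responder, and the follow-up arrangements make it likely that some responses will still be running at the cut-off.

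The shells have no place to show how many responses were ongoing, and no date at which to stop the clock for them. A programmer filling the tables would have to make an unwritten choice.

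What is at stake is how a positive cohort is described. A cohort can be declared positive on 3 responses in 24, and DoR is the result that tells the reader what those responses were worth.

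**Working it through.** **Plan's own figures.** The plan gives no number for DoR. Its Simon rule (at least 1 of 9, then at least 3 of 24; 5% against 20%) reproduces exactly, with one-sided alpha 0.0931 and power 0.8047. It matters here only for the number of responders: at least 3 in a positive cohort, and 24 × 0.20 = 4.8 expected at the target rate.

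**Inputs from the documents.** Recruitment lasts 24 months (protocol synopsis). The cut-off is 12 months after the last inclusion (protocol 6.5, 8.2.4.2). The first scheduled scan is at week 12, so t0 = 84/30.4375 = 2.76 months.

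**Assumptions, not in the documents.** DoR is exponential with true median m = 6 or 12 months, accrual is uniform, and response is first documented at week 12.

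**Follow-up after response.** This is uniform from a = 12 − 2.76 = 9.24 to b = 36 − 2.76 = 33.24 months.

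**Share ongoing at cut-off.** With λ = ln 2 / m, p = (e^(−λa) − e^(−λb)) / (λ(b − a)).
- m = 6 (λ = 0.1155): (0.344 − 0.021) / 2.773 = 0.116
- m = 12 (λ = 0.0578): (0.586 − 0.147) / 1.386 = 0.317

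**Mean if ongoing responses are counted as ended.** E[min(T, C)] = (1 − p)/λ, so the mean falls short by exactly the ongoing share.
- m = 6: 8.66 × (1 − 0.116) = 7.65, against a true 8.66
- m = 12: 17.31 × (1 − 0.317) = 11.82, against a true 17.31

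**Median on the same reading.** Solve e^(−λt) × P(C > t) = 0.5.
- m = 6: every responder is followed for at least 9.24 months, so the median stays at 6.00
- m = 12: at t = 10.82, 0.535 × (33.24 − 10.82)/24 = 0.500, so the median reads 10.82

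**Chance that a cohort has at least one ongoing response.** 1 − (1 − p)^n gives 31% / 68% with 3 responders and 46% / 85% with 5, for m = 6 / 12.

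**Coverage of the t-interval for the mean, 5 responders (200,000 simulated cohorts).** The interval contains the true mean in 88% / 74% of cohorts, against 88% with no censoring. The shortfall from 95% without censoring reflects skewness and small n; the fall to 74% is due to censoring.

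**Later response.** With first response at week 24 (t0 = 5.52 months), the ongoing share is 16% / 37%, the mean 7.27 / 10.87, the median 6.00 / 9.59, and coverage with 5 responders 86% / 65%.

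**Kaplan-Meier on the same data.** In a large sample, censoring the ongoing responses returns medians of 6.0 and 12.0.

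**The case against.** The strongest reply is that SAP section 1.5 already covers DoR. Kaplan-Meier censors a responder without an event, so a careful analyst would do so. This stands in part: a reader might infer that the plan has no rule at all for ongoing responses, and that goes too far. What is missing is a censoring date and a table that matches the rule.

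Counting ongoing responses as ended is nowhere instructed, so the figures show what happens if the shells are filled literally. That is fair, and they should be read as an illustration. A median with quartiles, or a restricted mean, could also come from a Kaplan-Meier fit. The shells do not say so, and the SD has no such reading.

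Three stronger inferences are not supported:

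- **Ongoing responses would be dropped as missing.** SAP section 1.4.4 is a no-imputation rule for missing data and drop-outs, and does not clearly direct this. It would be worse (mean 6.51 / 8.69, median 5.05 / 7.23).
- **DoR would be counted from first dose.** Section 1.5 does say "Time to event is derived relative to the first study treatment administration", but DoR's start at first CR or PR is explicit in every definition, and the specific definition prevails.
- **The death component contradicts PFS.** DoR counts cancer deaths and PFS counts any death. The DoR wording is consistent throughout, so this is a choice of event. Only the handling of other deaths needs stating.

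It is also true that individual data will be listed, so a reader could probably identify ongoing responses among 3 to 5 patients. That softens the problem but does not correct the summary.

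**Conclusion.** The concern holds. Tables 178 and 179 do not implement the SAP's own Kaplan-Meier rule, and DoR has no censoring date. Filled as ordinary summaries, the mean is too short by the share of responses still ongoing.

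Under the stated assumptions that is about 1 month at a true median of 6 (8.66 − 7.65 = 1.01), with the median and the coverage essentially unchanged. At a true median of 12 it is about 5.5 months (17.31 − 11.82 = 5.49), with coverage down to 74%. The documents give no expected DoR, so neither scenario can be preferred. The direction of the bias does not depend on the exponential shape; its size does.

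DoR is descriptive and untested. A reader might infer that the response-rate conclusion is at risk, but the Simon decision uses response counts only and is untouched. This should be corrected before the tables are filled; it does not threaten the trial's primary result.

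**What to change.** Replace the two shells with: responders, events, number censored, and Kaplan-Meier median with 95% CI. State the interval method for the median, because the log-log interval in SAP 2.5.2.2 is specified for the 6-month PFS rate. Kaplan-Meier quartiles and 6- and 12-month rates may be added if labelled, and a curve would complete the section 1.5 rule. Remove the ordinary mean, SD and CI of the mean, or replace the mean with a labelled restricted mean from the Kaplan-Meier fit.

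Add one rule: responders without an event are censored at the last available image, as for PFS.

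As clarifications, add a sentence that the first-dose time origin in section 1.5 does not apply to DoR, and a sentence on how deaths from other causes are handled.

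The cost is two shells and a few sentences, mostly adapted from the PFS section. The downside is precision. With 3 to 5 responders the Kaplan-Meier estimates will be wide, and at a true median of 12 months with week-12 response the median would not be reached in about 14% of cohorts with 5 responders and 19% with 3 (simulated). The SAP should say so.
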